2.2.1 Inclusion Criteria

Inclusion criteria: (1) Age between 7 years 0 months to 16 years 11 months. (2) Diagnosed with ADHD at the clinic of the Child psychology department, with Combined Presentation or Predominantly Hyperactive-Impulsive Presentation. (3) Doctor version of SNAP-IV Hyperactivity/Impulsivity score ≥ 12 . (4) Full-Scale Intelligence Quotient ≥ 80 (Wechsler intelligence scale for children-IV). (5) Resident in Shanghai, Zhejiang province, and Jiangsu province. (6) The parents or caregivers can understand the content of the study, are willing to participate in the follow-up visits, and complete the required information.

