2.15 Statistical methods

2.15.1 Statistical methods for primary and secondary outcomes

The primary outcome is a continuous variable: Hyperactivity/Impulsivity score change in the SNAP-IV scale. The primary analysis will be based on the intention-to-treat (ITT) population. The generalized linear model (GLM) will be used to test the difference 3 months after allocation between the groups. The estimated means and two-sided 95% confidence intervals (CI) will be derived. All secondary outcomes will be analyzed for a superiority-designed trial and two-sided significance with alpha=5% and standard 95% CIs for the treatment differences in these outcomes between the two treatment groups. Secondary outcome analyses will be based on the ITT population unless specified. SAS (version 9.4) will be used to perform all data analyses and generate the majority of data displays. STATA® (version 16.0) or SPSS, S-Plus, or R may also be used for data analyses and for generating statistical graphs. The other outcome measures will be calculated and presented with the same method of primary and secondary outcomes. Continuous variables will be summarized according to the number of subjects with non-missing data (n), mean, standard deviation (SD), median, minimum, maximum, and range interquartile (IQR). The confidence intervals will be reported on summaries of continuous effectiveness variables. Categorical variables will be summarized according to the absolute frequency and percentage of subjects (%) in each category level. The denominator for the percentages is the number of subjects in the treatment arm with data available unless noted otherwise.

Detailed information is displayed in the SAP.

2.15.2 Plans to give access to the complete protocol, participant-level data, and statistical code

The datasets used and analyzed during this trial can be granted access by the corresponding author and the safety monitoring board(DSMB) of CTU upon reasonable written request.

3 Oversight and monitoring

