### 2.2. Outcomes

#### 2.2.1. Primary outcome

Hyperactivity/Impulsivity score change assessed by doctor version of SNAP-IV scale at 3th month.

Time Frame: Baseline, 3th month after initiation of intervention

Type: repeated measured continuous variable

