## **5. Statistical Analyses**

### **5.1. Primary Outcome Analysis**

#### **5.1.1. ITT analysis of the primary outcome - the primary analysis**

The primary outcome is a repeated measured continuous variable, Hyperactivity/Impulsivity score change in doctor rated SNAP-IV scale. The primary analysis will be based on the mITT population as defined above. Generalized liner

mixed model (GLMM) will be performed using maximum likelihood (ML) method with treatment (binary) and time (ordinal) and interaction of treatment with time as fixed effect, and ID as random effect. Gaussian distribution and identity link function will be used in the GLMM model. Mean difference and 95% confidence intervals (CI) between groups at each time point will be estimated based on the fitted GLMM model.

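### The primary mixed model makes the 3-month confidence interval depend on the variance at other visits, in a direction the documents do not settle, and leaves out the baseline score

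*SAP*

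**What the plan says.** SAP 5.1.1 specifies a Gaussian, identity-link mixed model that "will be performed using maximum likelihood (ML) method". The section lists the model terms as follows: "with treatment (binary) and time (ordinal) and interaction of treatment with time as fixed effect, and ID as random effect". It names no residual covariance structure, degrees-of-freedom method or robust standard error.

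The response is described thus: "The primary outcome is a repeated measured continuous variable, Hyperactivity/Impulsivity score change in doctor rated SNAP-IV scale". The promised output is: "Mean difference and 95% confidence intervals (CI) between groups at each time point will be estimated based on the fitted GLMM model". The table shells in SAP 6.2 show changes from baseline at 3 and 6 months only. SAP 2.2.1, however, gives "Time Frame: Baseline, 3th month after initiation of intervention" and calls the outcome repeatedly measured, and the variable list in SAP 7 holds raw scores at baseline, 3 and 6 months. Whether a baseline row enters the response is therefore not stated.

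The covariate-adjusted model in SAP 5.1.3 lists sex, height, weight, age, IQ, prior exercise time and medication, but not the baseline hyperactivity/impulsivity (H/I) score. Protocol 2.15.1 names another model: "The generalized linear model (GLM) will be used to test the difference 3 months after allocation between the groups".

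**The concern.** A single random intercept gives all visits one variance and all pairs of visits one correlation. The standard error of the 3-month contrast is then built from a variance averaged over visits, so it is right only when the visits happen to agree.

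There are reasons to doubt that they do. Month 6 is a secondary outcome (SAP 2.2.2), and Protocol 2.5.3 permits sensory integration and behavioral therapy once the 3-month visit is complete, so its variance may differ from that at month 3. If baseline is a response row, its spread is restricted by the entry rule: Protocol 2.2.1 requires the "Doctor version of SNAP-IV Hyperactivity/Impulsivity score" to be at least 12 on a 0–27 scale.

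At stake are the coverage and the two-sided 5% error rate of the trial's one confirmatory test. Omitting a baseline score that every participant must have also gives up precision.

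**Working it through.** **Planned figures.** From SAP 3.6: difference 3.1, SD of change 5.8, two-sided 0.05, 80% power. The normal approximation gives 2 × (1.960 + 0.842)² × 5.8² / 3.1² = 55 per arm. Noncentral-t power is 79.3% at 55 and 80.05% at 56, so the stated 56 is reproduced. 56/0.95 rounds up to 59 per arm, 118 in total; the stated 120 is a multiple of the block size of 4. The planned SE at 3 months is 5.8 × √(2/56) = 1.096.

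**Case A: response is change at 3 and 6 months.** With two visits only the equal-variance constraint bites. On balanced data the ratio of reported to true SE at 3 months is √[(s₃² + s₆²)/2] / s₃, and coverage is 2Φ(1.96 × ratio) − 1. Take s₃ = 5.8; s₆ is an assumption.

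| Month-6 SD | SE ratio | Coverage |
|---|---|---|
| 4.0 | 0.859 | 90.8% |
| 4.8 | 0.918 | 92.8% |
| 5.8 | 1.000 | 95.0% |
| 6.5 | 1.062 | 96.3% |
| 7.5 | 1.156 | 97.7% |

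First row: √[(33.64 + 16)/2] / 5.8 = 4.98/5.8 = 0.859. A correct half-width of 1.96 × 1.096 = 2.15 would be reported as anything from 1.85 to 2.48. Simulation (400 trials per setting, 56 per arm) agrees: mean SE 0.994 against an empirical SD of 1.140 for s₆ = 4.8, and 1.146 against 1.065 for s₆ = 6.5.

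**Case B: response is raw score at 0, 3 and 6 months.** The model sets the variance of every between-visit difference to the mean of the three pairwise variances. Assume SDs 4/5.5/5.5 and correlations 0.3 (0–3), 0.3 (0–6) and 0.7 (3–6):
- 0–3 and 0–6: 16 + 30.25 − 2 × 0.3 × 4 × 5.5 = 33.05 each (change SD 5.75, close to the planned 5.8).
- 3–6: 60.5 − 2 × 0.7 × 30.25 = 18.15.
- Mean 28.08; SE ratio √(28.08/33.05) = 0.92.
- Type I error 2[1 − Φ(1.96 × 0.92)], about 7.1%, or 7.3% with the ML factor below. Simulation gave 7.4%.

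Over a grid (baseline SD 3.0–4.5, later SD 5.0–6.0, 3–6 correlation 0.4–0.8, change SD held at 5.8) the ratio for the 3-month change contrast runs from 0.875 to 1.046:
- Low end, later SD 5.0 and correlation 0.8: √[(2 × 33.64 + 10)/3 / 33.64] = 0.875.
- High end, later SD 6.0 and correlation 0.4: √[(2 × 33.64 + 43.2)/3 / 33.64] = 1.046.

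**ML.** At N = 112 the ML-to-REML SE ratio is √(110/112) = 0.991. Using z in place of t as well makes the interval about 2% too narrow (coverage about 94.5%).

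**Baseline score.** Residual variance with baseline as covariate is s₃²(1 − r²), with r the 0–3 correlation; for the plain change score it is that amount plus (slope − 1)² × s₀², so adjustment never does worse apart from one degree of freedom. With the Case B example: 30.25 × (1 − 0.09) = 27.53 against 33.05, an SE ratio of √0.833 = 0.91. This depends on the assumed correlation.

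**The case against.** The strongest reply is that SAP 5.1.1 names score change as the response and the table shells show only months 3 and 6. On that reading, the inputs that give 7% error for raw scores give a change SD of 5.75 at both visits. The random intercept is then exactly right and the SE ratio is 1.00. This stands, and so does the absence from the documents of any month-6 SD, raw-score SD or between-visit correlation.

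A reader might infer that the planned interval is too narrow and the type I error inflated. Some details do hint at a baseline row: two-level variables are labelled binary while time is called ordinal, and only raw scores are listed as variables. On that reading the difference in 3-month level, as opposed to change, had SE ratios of 0.866 to 0.968 throughout the grid. But this is the less literal reading, and the change contrast, which is what the hypothesis in SAP 4.1 tests, can go either way. Later therapy could as easily raise the month-6 variance and widen the interval.

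A reader might also infer that ordinal time will be entered as a number and shrink the 3-month difference. With three rows and a true 3-month difference of 3.1, a straight line would give (0 + 3.1 + x)/3, or 1.03 to 2.07 for a 6-month difference x of 0 to 3.1. That needs both numeric coding and a baseline row. The SAP labels its numeric covariates continuous, does not so label time, and promises a difference at each time point, so factor coding is the natural reading. With change at two visits, numeric time reproduces 3.10 exactly.

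Finally, Protocol 2.15.1 defers detail to the SAP. It still names a different model for the same test.

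**Conclusion.** The dependence is real; its direction is not established. As written, the 3-month interval is correct only if the visits share a variance (and, with a baseline row, a common correlation). Otherwise the SE is off by a factor of about 0.86 to 1.16 (change scores, assumed month-6 SD 4.0 to 7.5) or 0.875 to 1.046 (raw scores, change contrast). The only SDs the documents give are for 3-month change (5.81, 3.72 and the planning value 5.8); every other SD and correlation here is assumed. ML is a minor contributor. The omission of baseline H/I is certain from the text, while the precision lost depends on an unknown correlation. The documents do not show that the planned test is anti-conservative or its estimate biased.

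**What to change.** In SAP 5.1.1, state that the response is the doctor-rated H/I score (or its change) at 3 and 6 months. Enter visit as a categorical factor, with treatment, treatment by visit and baseline H/I as covariate. Use an unstructured within-subject covariance and REML with Kenward-Roger degrees of freedom. Name the treatment contrast at the 3-month visit as the primary estimate. Amend Protocol 2.15.1 to name the same model.

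With baseline as a covariate there are two response visits, so the unstructured matrix has 3 parameters (two variances, one covariance) against 2 for the random intercept. The cost is SAP and protocol wording and a few program lines. The planned 56 per arm and 120 in total are unaffected.

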### **5.1.2. Per-protocol analyses of the primary outcome**

Per-protocol analysis will also be performed by using GLMM model (as described in 5.1.1).

### **5.1.3. Covariate adjusted analysis of the primary outcome**

An analysis of the primary outcome will be adjusted for, sex (binary), admission height(continuous), admission weight (continuous), admission age (continuous), admission IQ score (continuous), regular exercise time prior to admission(continuous) and admission medical usage (using medicine or not when enrolled, binary) of the primary outcome by GLMM model (as described in 5.1.1).

If the above GLMM model does not converge, GLMM model will be performed with less covariates until coverage.

Covariate adjusted analysis will be performed on both mITT and PP populations.

### **5.1.4. Subgroup analyses of the primary outcome**

Subgroup analyses will be performed for the primary outcome if each subgroup contains enough subject after stratification. We will stratify by sex (binary), categorized baseline medication usage (using medicine or not when enrolled, binary), qualified exercise days (less than 30/36/42/48 days, respectively, binary), categorized baseline exercise habit(binary), categorized baseline WFIRS score, and categorized baseline

SNAP score, respectively. (According to the scale rules, the continues variable will be transformed to the categorical variable.)

Subgroup analyses will be performed on both mITT and PP populations.

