2.4.2 Intervention description

The Baduanjin exercise group is asked to use the Baduanjin training system to practice the whole set of Baduanjin at least once a day and at least 5 days each week for 3 months. The Baduanjin training system is a video game designed with motion tracking and motion recognition strategy by the research team, providing a motivating full-body interactive experience for children with ADHD to engage in practice. Caregivers included in the Baduanjin intervention group were equipped with a Kinect sensor bar, connector, and software package on the day of enrolment. The software and electronic equipment installation is guided by researchers on the same day in the

hospital and at their homes later if necessary.

During the study, the children were asked to practice Baduanjin using the given software for at least 30 minutes daily, 5 times each week. They can practice any single brocade or the whole combination of 8 movements using the different game modes in the software. Instructions for movements and the variety of breath are provided in each game mode. The eight movements of Baduanjin are listed as follows:

1. Hold up the hands to regulate the triple burner;
2. Draw a bow like shooting a hawk;
3. Raise one arm to regulate the spleen and stomach;
4. Turn the head back to treat consumptive diseases and injuries;
5. Sway the head and swing the buttocks to expel the heart-fire;
6. Hold the feet by the hands to reinforce the loins and kidneys;
7. Punch with anger;
8. Hold and drop the heels to improve the health of the spine.

During their exercise, the child's motion will be captured and projected onto the screen, and their movement will be scored according to accuracy. The advice on motion adjustment is given immediately, and the feedback of data will be shown on the screen after each round of the game, then uploaded to a management website to be monitored by researchers.

The children in the Baduanjin group were asked to use the fitness tracker and uploaded data the same as the control group. The time of exercise is required to exceed 30 minutes each time, and the maximum heart rate during the exercise should be over 120 beats per minute. Researchers will also check with the data uploaded automatically by the Baduanjin software to ensure the movements are adequately practiced.

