2.5.1 Strategies to improve adherence to interventions

In this trial, each family has a Wechat discussion group where they can upload their biological data and contact the researcher conveniently. Researchers will check the uploaded data every

morning and give feedback to caregivers in the discussion group. When the data is not uploaded, researchers will remind the caregivers to upload data and make sure that if they have any difficulty in continuing the exercise. Researchers will also check the data uploaded automatically by the Baduanjin software to ensure the movements were adequately practiced. When unqualified exercise data is identified, the researcher will contact the caregiver to modify their exercise status and guide them to meet the requirement of exercise intensity and movement accuracy.

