2.5.2 Definition of adherence

Researchers will check the uploaded data every day. If the time of exercise exceeds 30 minutes, and the maximum heart rate during the exercise is over 120 beats per minute, it is recorded as a day that meets the adherence standard. For the participants in the Baduanjin group, the score automatically rated by the Baduanjin software should also exceed 77.5. We require the participants to meet the adherence standard for at least 5 days each week. Participants that finished less than 80% required days are defined as having poor adherence.

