#### *-Per-protocol population*

Participants will be excluded from the per-protocol population if their qualified exercise days (more than 30 minutes and the maximum heart rate during the exercise should be over 120 beats) less than 48 days. The experimental group in the per-protocol analysis will be defined according to what the participant actual receive. This population will be used for the supportive analyses.

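### SAP 5.1.4 stratifies the primary between-arm comparison by qualified exercise days, which are observed after randomisation, without labelling it non-randomised; for the baseline factors it names no treatment-by-subgroup interaction

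*SAP*

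**What the plan says.** SAP 5.1.4 plans subgroup analyses of the primary outcome by sex, baseline medication use, baseline exercise habit, baseline WFIRS, baseline SNAP and "qualified exercise days (less than 30/36/42/48 days, respectively, binary". They are to be run "if each subgroup contains enough subject after stratification"; how many is enough is not stated. The section adds: "Subgroup analyses will be performed on both mITT and PP populations".

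The contrast is not written out. The only contrast the SAP gives for this outcome is the mean difference between groups at each time point (SAP 5.1.1), so the natural reading is a between-arm difference within each stratum. The only interaction named anywhere in the SAP is treatment with time, also in 5.1.1.

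Protocol 2.5.2 describes a daily check of uploaded data; if duration and heart rate reach the threshold, "it is recorded as a day that meets the adherence standard". SAP 4.2 uses the same kind of count to define the per-protocol set: "Participants will be excluded from the per-protocol population if their qualified exercise days" number fewer than 48. Of that set it says: "This population will be used for the supportive analyses". SAP 5.1.4 gives the exercise-day strata no comparable label.

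**The concern.** A subgroup analysis keeps the protection of randomisation only if membership is fixed before allocation. Sex and the baseline factors meet that condition. Qualified exercise days do not: each child earns them while doing the assigned exercise. The Baduanjin children who reach a given count and the control children who reach it may differ in prognosis, and a between-arm difference inside the stratum then mixes treatment effect with selection.

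The protocol gives some reason to think adherence might differ. Only the Baduanjin arm has the game, described as "providing a motivating full-body interactive experience for children with ADHD to engage in practice", and only that arm has a second source of practice data: "Researchers will also check the data uploaded automatically by the Baduanjin software to ensure the movements were adequately practiced".

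The baseline factors raise a separate issue. Subgroups are informative when the effects are compared with each other. If the output is one result per stratum and no interaction estimate, a reader is left to compare stratum results by eye, and in a trial of this size those often look discordant by chance alone.

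**Working it through.** **1. The plan's own figure.** Inputs from SAP 3.6: difference 3.1, SD 5.8, two-sided 0.05, 80% power, 56 per arm. SE = 5.8 × √(2/56) = 1.10, and the two-sample t test has 80.1% power. The sample size reproduces. A t test on the 3-month change stands in for the mixed model here and below.

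**2. Separate subgroup results when the effect is uniform.** Assume a true effect of 3.1 and SD 5.8 in both strata. With stratum powers p and q, the chance that exactly one is significant is p(1 − q) + q(1 − p). The split ratios are assumptions.

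| Split | Per arm in each stratum | Power in each | Exactly one significant |
|---|---|---|---|
| 50:50 | 28 / 28 | 50.2% / 50.2% | 50% |
| 30:70 | 16.8 / 39.2 | 32.4% / 64.7% | 55% |
| 20:80 | 11.2 / 44.8 | 22.6% / 70.6% | 61% |

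For example, at 20:80: 0.226 × 0.294 + 0.706 × 0.774 = 0.61.

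**3. What an interaction estimate would offer.** SE = 5.8 × √(2/n1 + 2/n2), with n1 and n2 the per-arm stratum sizes. Power for an interaction of 3.1 is Φ(3.1/SE − 1.96). The size detectable with 80% power is 2.80 × SE.

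| Split | SE | Power for 3.1 | Detectable with 80% power |
|---|---|---|---|
| 50:50 | 2.19 | 29% | 6.1 |
| 30:70 | 2.39 | 25% | 6.7 |
| 20:80 | 2.74 | 20% | 7.7 |

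**4. Exercise-day strata: illustration only.** Every adherence input here is an assumption, because the documents give none. Let days be normal with SD 10, correlated r with the change score within arm (improvement counted as positive), and let the true effect be 3.1 everywhere. Cut at 48, which is 47.5 after rounding to whole days. The bias in a stratum is 5.8 × (r_B × z_B − r_C × z_C), where z is the mean standardised days of that arm's children in that stratum.

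Worked case: mean days 51 in Baduanjin and 45 in control, r = 0.3 in both. In the upper stratum z_B = 0.589 and z_C = 0.964, so the bias is 5.8 × 0.3 × (0.589 − 0.964) = −0.65.

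| Mean days, Baduanjin / control | r, Baduanjin / control | Bias below 48 | Bias at 48 or more |
|---|---|---|---|
| 48 / 48 | 0.3 / 0.3 | 0 | 0 |
| 51 / 45 | 0 / 0 | 0 | 0 |
| 54 / 51 | 0.1 / 0.1 | −0.13 | −0.09 |
| 51 / 45 | 0.2 / 0.2 | −0.45 | −0.43 |
| 51 / 45 | 0.3 / 0.3 | −0.67 | −0.65 |
| 45 / 51 | 0.3 / 0.3 | +0.67 | +0.65 |
| 54 / 42 | 0.3 / 0.3 | −1.34 | −1.29 |
| 48 / 48 | 0.3 / 0 | −1.44 | +1.33 |

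The bias can be zero or of either sign. In the last row the effect appears to grow with adherence although it is uniform.

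**5. Per-protocol set.** Membership requires at least 48 qualified days. The groups below 30, 36, 42 and 48 days are therefore all empty, and the factor does not divide that population.

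**The case against.** Five points can be made for the plan.

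- The exercise-day factor is recognisable. The other factors are marked as baseline or at enrolment, or, like sex, are plainly fixed, and SAP 4.2 describes qualified days as exercise done in the trial. A reader might infer that the SAP passes adherence strata off as ordinary subgroups. The text does not support that: a careful reader can tell them apart, and SAP 5.1.1 reserves the primary analysis for the mITT comparison. What is missing is a statement of how the result should be read.
- Adherence support is not one-sided. Both arms have trackers and daily data checks (Protocol 2.4.1, 2.4.2, 2.5.1) and the same coins, prizes and medals (Protocol 2.12.2), and control children choose an activity they like (Protocol 2.4.1). The software-score condition in Protocol 2.5.2, if applied to the count, would lower Baduanjin days, whereas the game might raise them. It would therefore be wrong to infer that the strata favour one arm. This objection stands in full.
- The bias figures depend on invented inputs. This also stands. A 6-day gap with r of 0.2 to 0.3 gives 0.4 to 0.7 points, under half the within-stratum SE of 1.55 at 28 per arm. The values near 1.3 to 1.4 need a 12-day gap, or a correlation in one arm only; nothing in the documents points to either.
- The SAP has no rule for comparing p-values across strata, and two disjoint strata with CIs allow a rough interaction calculation. That is correct, but the plan neither reports that calculation nor says it should be made.
- The interaction test is weak. That is true, and it is a reason to show the estimate with its CI, because the width makes the uncertainty visible.

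**Conclusion.** The point holds as a modest fix to the secondary analyses. SAP 5.1.4 uses a variable observed after randomisation to stratify a between-arm comparison and does not label the result non-randomised or exploratory. The bias cannot be sized from the documents, its direction is unknown, and it may be zero. The emptiness of the lower strata in the per-protocol set is a drafting fault; it produces no wrong result.

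For the baseline factors no treatment-by-subgroup interaction is named. Under a uniform effect of 3.1, SD 5.8 and 56 per arm, separate stratum results disagree on significance in about 50% to 61% of trials, depending on the split. That range assumes equal SD across strata and a t test in place of the mixed model.

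A reader might go further and infer that the trial's main result is compromised. It is not: the primary mITT comparison and the sample size use none of these strata.

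**What to change.** 1. Take qualified exercise days out of the SAP 5.1.4 subgroup list. If the question is kept, report it as a separate analysis in the mITT set, labelled non-randomised and exploratory. In either case tabulate the distribution of qualified days by arm.
2. For sex, medication, exercise habit, WFIRS and SNAP, report the treatment-by-subgroup interaction at 3 months with its CI, from one mITT model per factor. Label these analyses exploratory and state that their power is low.
3. Reconcile Protocol 2.5.2 with SAP 4.2. The protocol adds a software-score condition to a qualifying day in the Baduanjin arm; the SAP definition does not mention it. The count needs one stated meaning.

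The cost is SAP wording and a little more analysis, with no new data. The interaction results will usually be inconclusive at this size. Dropping the day strata gives up an adherence-stratified comparison; relabelling keeps it, but it remains non-randomised.
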